### **7.1.6. Summaries of Adverse Events and Deaths**

Treatment-emergent AEs will be summarized based on the Safety Analysis Set.

#### **7.1.6.1. Summaries of AE incidence in Combined Severity Grade Subsets**

The number and percentage of subjects who experienced at least 1 TEAE will be provided and summarized by SOC, HLT, PT, and treatment group. For other AEs described below, summaries will be provided by SOC, PT, and treatment group:

- TEAEs of Grade 3 or higher (by maximum severity)
- TEAEs of Grade 2 or higher
- All Treatment Emergent (TE) treatment-related AEs
- TE Treatment-related AEs of Grade 3 or higher (by maximum severity)
- TE Treatment-related AEs of Grade 2 or higher
- All TE SAEs
- All TE treatment-related SAEs
- All TEAEs leading to premature discontinuation of any study drug
- All TEAEs leading to premature discontinuation of study
- All TEAEs leading to death (ie, outcome of death)
- All TEAEs leading to temporary interruption of any study drug

A brief, high-level summary of AEs described above will be provided by treatment group and by the number and percentage of subjects who experienced the above AEs. All deaths observed in the study will be also included in this summary.

Multiple events will be counted only once per subject in each summary. Adverse events will be summarized and listed first in alphabetic order of SOC and HLT within each SOC (if applicable), and then by PT in descending order of total frequency within each SOC. For summaries by severity grade, the most severe grade will be used for those AEs that occurred more than once in an individual subject during the study.

In addition to the above summary tables, all TEAEs and TE treatment-related AEs will be summarized by PT only, in descending order of total frequency.

In addition, data listings will be provided for the following:

- All AEs, indicating whether the event is treatment emergent
- All AEs of Grade 3 or higher
- All AEs of Grade 2 or higher
- SAEs
- Deaths
- AEs leading to death (ie, outcome of death)
- AEs leading to premature discontinuation of any study drug
- AEs leading to premature discontinuation of study
- AEs leading to temporary interruption of any study drug

## 7.2. Laboratory Evaluations

Laboratory data collected during the study will be analyzed and summarized using both quantitative and qualitative methods. Summaries of laboratory data will be provided for the Safety Analysis Set and will include data collected up to the last dose of any study drug plus 30 days for subjects who have permanently discontinued study drug, or all available data at the time of the database snapshot for subjects who were ongoing at the time of an interim analysis. The analysis will be based on values reported in conventional units. When values are below the LOQ, they will be listed as such, and the closest imputed value will be used for the purpose of calculating summary statistics as specified in Section 3.7. Hemolized test results will not be included in the analysis, but they will be listed in by-subject laboratory listings.

A by-subject listing for laboratory test results will be provided by subject ID number and visit in chronological order for hematology, serum chemistry, coagulation, serology, lipid panel, and urinalysis separately. Values falling outside of the relevant reference range and/or having a severity grade of 1 or higher on the common terminology criteria for adverse events (CTCAE) severity grade will be flagged in the data listings, as appropriate.

No formal statistical testing is planned.

### **7.2.1. Summaries of Numeric Laboratory Results**

Descriptive statistics will be provided by treatment group for each laboratory test specified in the study protocol as follows:

- Baseline values
- Values at each postbaseline visit
- Change from baseline at each postbaseline visit

A baseline laboratory value will be defined as the last measurement obtained on or prior to the date/time of first dose of any study drug. Change from baseline to a postbaseline visit will be defined as the visit value minus the baseline value. The mean, median, Q1, Q3, minimum, and maximum values will be displayed to the reported number of digits; SD values will be displayed to the reported number of digits plus 1.

Median (Q1, Q3) of the observed values for selected laboratory tests will be plotted using a line plot by treatment group and visit.

In the case of multiple values in an analysis window, data will be selected for analysis as described in Section 3.7.3.

### **7.2.2. Graded Laboratory Value**

The CTCAE Version 4.03 (with one modification specified in protocol) will be used to assign toxicity grades (0 to 5) to laboratory results for analysis. Grade 0 includes all values that do not meet the criteria for an abnormality of at least Grade 1. For laboratory tests with criteria for both increased and decreased levels, analyses for each direction (ie, increased, decreased) will be presented separately.

#### **7.2.2.1. Treatment-Emergent Laboratory Abnormalities**

Treatment-emergent laboratory abnormalities are defined as values that increase at least 1 toxicity grade from baseline at any postbaseline time point, up to and including the date of last dose of any study drug plus 30 days for subjects who permanently discontinued study drug, or the last available date in the database snapshot for subjects who were still on treatment at the time of an interim analysis.

If the relevant baseline laboratory value is missing, any abnormality of at least Grade 1 observed within the time frame specified above will be considered treatment emergent.

#### 7.2.2.2. Treatment-Emergent Marked Laboratory Abnormalities

Treatment-emergent marked laboratory abnormalities are defined as values that increase from baseline by at least 3 toxicity grades at any postbaseline time point, up to and including the date of the last dose of any study drug plus 30 days for subjects who permanently discontinued study drug or the last available date in the database snapshot for subjects who were still on treatment at the time of an interim analysis.

If the relevant baseline laboratory value is missing, any Grade 3 or higher values observed within the timeframe specified above will be considered treatment-emergent marked abnormalities.

#### 7.2.2.3. Summaries of Laboratory Abnormalities

Laboratory data that are categorical will be summarized using the number and percentage of subjects in the study with the given response at baseline and each scheduled postbaseline visit.

The following summaries (number and percentage of subjects) for treatment-emergent laboratory abnormalities will be provided by lab test and treatment group; subjects will be categorized according to the most severe postbaseline abnormality grade for a given lab test:

- Graded laboratory abnormalities
- Grade 3 or higher laboratory abnormalities
- Marked laboratory abnormalities

For all summaries of laboratory abnormalities, the denominator is the number of subjects with nonmissing postbaseline values up to 30 days after last dosing date.

A by-subject listing of treatment-emergent Grade 3 or higher laboratory abnormalities and marked laboratory abnormalities will be provided separately by subject ID number and visit in chronological order. These listings will include all test results that were collected throughout the study for the lab test of interest, with all applicable severity grades or abnormal flags displayed.

#### 7.2.3. Liver-related Laboratory Evaluations

Liver-related abnormalities after initial study drug dosing will be examined and summarized using the number and percentage of subjects who were reported to have the following laboratory test values for postbaseline measurements:

- Aspartate aminotransferase (AST): (a)  $> 3$  times of the upper limit of reference range (ULN); (b)  $> 5 \times$  ULN; (c)  $> 10 \times$  ULN; (d)  $> 20 \times$  ULN
- Alanine aminotransferase (ALT): (a)  $> 3 \times$  ULN; (b)  $> 5 \times$  ULN; (c)  $> 10 \times$  ULN; (d)  $> 20 \times$  ULN
- AST or ALT: (a)  $> 3 \times$  ULN; (b)  $> 5 \times$  ULN; (c)  $> 10 \times$  ULN; (d)  $> 20 \times$  ULN

- Total bilirubin:  $> 2 \times \text{ULN}$
- Alkaline phosphatase (ALP)  $> 1.5 \times \text{ULN}$
- AST or ALT  $> 3 \times \text{ULN}$  and total bilirubin: (a)  $> 1.5 \times \text{ULN}$ ; (b)  $> 2 \times \text{ULN}$

The summary will include data from all postbaseline visits up to 30 days after the last dose of any study drug. For individual laboratory tests, subjects will be counted once based on the most severe postbaseline values. For both the composite endpoint of AST or ALT and total bilirubin, subjects will be counted once when the criteria are met at the same postbaseline visit date. The denominator is the number of subjects in the Safety Analysis Set who have nonmissing postbaseline values of all relevant tests at the same postbaseline visit date. A listing of subjects with AST or ALT  $> 3 \times \text{ULN}$  will be provided.

#### **7.2.4. Shifts Relative to the Baseline Value**

Shift tables will be presented by showing change in severity grade from baseline to postbaseline visits for the following laboratory tests:

- Complete blood count components
- Creatinine clearance (estimated glomerular filtration rate)
- Liver function tests
- Creatinine phosphokinase (CPK)
- CRP

#### **7.3. Body Weight and Vital Signs**

Descriptive statistics will be provided by treatment group for body weight, BMI and vital signs (systolic and diastolic blood pressures [mmHg], pulse [beats/min]) as follows:

- Baseline value
- Values at each postbaseline visit
- Change from baseline at each postbaseline visit

A baseline value will be defined as the last available value collected on or prior to the date/time of first dose of any study drug. Change from baseline to a postbaseline visit will be defined as the postbaseline value minus the baseline value. Body weight and vital signs measured at unscheduled visits will be included for the baseline value selection.

In the case of multiple values in an analysis window, data will be selected for analysis as described in Section 3.7.3. No formal statistical testing is planned.

A by-subject listing of vital signs (systolic and diastolic blood pressure [mmHg], pulse [beats/min], respiration [breaths/min], and body temperature [ $^{\circ}\text{C}$ ]) will be provided by subject ID number and visit in chronological order. In the same manner, a by-subject listing of body weight, height, and BMI will be provided separately.

#### **7.4. Prior and Concomitant Medications**

Medications collected at screening and during the study will be coded using the World Health Organization (WHO) Drug dictionary version Q22016.

All the analyses in this section will be performed for general prior /concomitant medications and RA-specific prior/concomitant medications separately, unless otherwise specified.

##### **7.4.1. Prior Medications**

Prior medications are defined as any medication taken before a subject took the first study drug.

Prior medications will be summarized by Anatomical Therapeutic Chemical (ATC) drug class Level 4 and preferred name using the number and percentage of subjects for each treatment group and overall. A subject reporting the same medication more than once will be counted only once when calculating the number and percentage of subjects who received that medication. The summary will be ordered alphabetically by ATC medical class and then by preferred name in order of descending overall frequency within each ATC medical class. For drugs with the same frequency, sorting will be done alphabetically.

For the purposes of analysis, any medication with a start date prior to the first dosing date of any study drug will be included in the prior medication summary regardless of when the stop date is. If a partial start date is entered the medication will be considered prior unless the month and year (if day is missing) or year (if day and month are missing) of the start date are after the first dosing date. Medications with a completely missing start date will be included in the prior medication summary, unless otherwise specified.

Summaries will be based on the Safety Analysis Set. No formal statistical testing is planned.

##### **7.4.2. Concomitant Medications**

Concomitant medications are defined as medications taken while a subject took study drug. Use of concomitant medications will be summarized by ATC drug class Level 4 and preferred name using the number and percentage of subjects for each treatment group. A subject reporting the same medication more than once will be counted only once when calculating the number and percentage of subjects who received that medication. The summary will be ordered alphabetically by ATC medical class and then by preferred name in descending overall frequency within each ATC medical class. For drugs with the same frequency, sorting will be done alphabetically.

For the purposes of analysis, any medication with a start date prior to or on the first dosing date of any study drug and continued to take after the first dosing date, or started after the first dosing date but prior to or on the last dosing date of study drug will be considered concomitant medications. Medications started and stopped on the same day as the first dosing date or the last dosing date of any study drug will also be considered concomitant. Medications with a stop date prior to the date of first dosing date of any study drug or a start date after the last dosing date of any study drug will be excluded from the concomitant medication summary. If a partial stop date is entered, any medication with the month and year (if day is missing) or year (if day and month are missing) prior to the date of first study drug administration will be excluded from the concomitant medication summary. If a partial start date is entered, any medication with the month and year (if day is missing) or year (if day and month are missing) after the study drug stop date will be excluded from the concomitant medication summary. Medications with completely missing start and stop dates will be included in the concomitant medication summary, unless otherwise specified.

Summaries will be based on the Safety Analysis Set. No formal statistical testing is planned.

All prior and concomitant medications will be provided in a by-subject listing sorted by subject ID number and administration date in chronological order.

## **7.5.                   Electrocardiogram Results**

### **7.5.1.               Investigator Electrocardiogram Assessment**

A shift table of the investigators' assessment of ECG results at each visit compared with baseline values will be presented by treatment group using the following categories: normal; abnormal (not clinically significant); abnormal (clinically significant); or missing. The number and percentage of subjects in each cross-classification group of the shift table will be presented. Subjects with a missing value at baseline or postbaseline will not be included in the denominator for percentage calculation.

No formal statistical testing is planned.

A by-subject listing for ECG assessment results will be provided by treatment group and subject ID number and visit in chronological order.

### **7.5.2.               Corrected QT Intervals**

The QT interval (measured in millisecond [msec]) is a measure of the time between the start of the Q wave and the end of the T wave in the heart's electrical cycle. The QT interval represents electrical depolarization and repolarization of the ventricles. The QT interval is affected by heart rate, and a number of methods have been proposed to correct QT for heart rate.

Corrected QT (QTc) intervals will be derived using Fridericia's correction (QTcF) as follows:

$$QTcF = \frac{QT}{\sqrt[4]{RR}}$$

where QT is measured in msec; RR = 60/Heart Rate (beats per minute [bpm]) and RR is measured in seconds

QTcF and uncorrected QT values at each visit and change from baseline at each visit will be summarized for the Safety Analysis Set by treatment group using descriptive statistics.

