## LIST OF ABBREVIATIONS

ACR	American College of Rheumatology
ACR 20/50/70	American College of Rheumatology 20/50/70% improvement
AE	adverse event
ALT	alanine aminotransferase
AST	aspartate aminotransferase
ATC	anatomical therapeutic chemical drug class
AUC	area under the curve
bDMARD	biological disease modifying anti-rheumatic drug
BLQ	below the limit of quantitation
BMI	body mass index
BPM	beats per minute
CDAI	clinical disease activity index
CI	confidence interval
CMH	Cochran-Mantel-Haenszel
CRF	case report form
CRP	C-reactive protein
CPK	creatinine phosphokinase
CSR	clinical study report
CTCAE	common terminology criteria for adverse events
DAS28	disease activity score for 28 joint count
ECG	electrocardiogram
eCRF	electronic case report form
FAS	full analysis set
Gilead	Gilead Sciences
HAQ-DI	health assessment questionnaire-disability index
HLGT	high-level group term
HLT	high-level term
ID	identification
IXRS	interactive web and mobile response system
JAK	janus kinase
LLOQ	lower limit of quantitation
LLT	lower-level term
LOCF	last observation carried forward
LOQ	limit of quantitation
MedDRA	medical dictionary for regulatory activities
MMRM	mixed model repeated measures
MTX	methotrexate
NRI	non-responder imputation

---

PhGA	physician's global assessment
PT	preferred term
PtGA	patient's global assessment
PK	pharmacokinetic
POC	proof-of-concept
PTM	placebo-to-match
Q1, Q3	first quartile, third quartile
QD	quaque die (each day)
QT	electrocardiographic interval between the beginning of the Q wave and termination of the T wave, representing the time for both ventricular depolarization and repolarization to occur
QTc	corrected QT
QTcF	corrected CT interval using the Fridericia formula
RA	rheumatoid arthritis
SAE	serious adverse event
SAP	statistical analysis plan
SD	standard deviation
SDAI	simplified disease activity index
SE	standard error
SJC	swollen joint count
SOC	system organ class
SYK	spleen tyrosine kinase
TE	treatment-emergent
TEAE	treatment-emergent adverse event
TFs	tables, figures, and listings
TJC	tender joint count
ULN	upper limit of normal
VAS	visual analog scale
WHO	World Health Organization

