#### **7.5.3. PR and QRS Intervals**

The PR interval (measured in msec) is a measure of the time between the start of the P wave (the onset of atrial depolarization) and the beginning of the QRS complex (the onset of ventricular depolarization). The QRS interval measures the duration of the QRS complex.

VR, PR, RR, and QRS values at each visit and change from baseline at each visit will be summarized for the Safety Analysis Set by treatment group using descriptive statistics.

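### Does the QTcF equation in SAP Section 7.5.2 use the wrong root of RR?

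*SAP*

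**What the plan says.** SAP Section 7.5.2 names the method before it shows any equation: "Corrected QT (QTc) intervals will be derived using Fridericia"'s correction, abbreviated QTcF. The list of abbreviations ties QTcF to the same method, as the corrected "interval using the Fridericia formula", and gives no exponent. Below the displayed equation, Section 7.5.2 fixes the units: QT in milliseconds, and "RR = 60/Heart Rate (beats per minute [bpm]) and RR is measured in seconds".

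The use of the result is also stated there: "QTcF and uncorrected QT values at each visit and change from baseline at each visit will be summarized for the Safety Analysis Set". These summaries are descriptive and given for each arm. Section 7.5.3 adds that "VR, PR, RR, and QRS values at each visit and change from baseline at each visit will be summarized", and Section 7.3 summarizes pulse. Section 7.5 specifies no hypothesis test on QTcF and no QTcF threshold categories.

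**The concern.** In text extracted from the PDF, the equation under the naming sentence has a radical with index 4 over RR. The standard definition of the Fridericia correction has index 3. Name and equation would then disagree, and because the sentence introduces the equation as the way the value is derived, a programmer might code the equation and not the name.

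If that happened, output labelled QTcF would not be Fridericia QTcF. The value would be too low above 60 bpm and too high below it. Change from baseline would also carry a heart-rate artefact: a rise in heart rate would appear as a shortening of QTcF and could partly hide a real prolongation. QTcF is the only rate-corrected interval the SAP plans, so it is reasonable to ask.

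**Working it through.** **Inputs.** From SAP Section 7.5.2: QT in ms and RR = 60/HR in seconds. From the extracted equation: exponent 1/4. From the standard definition of the named method, not written out in the SAP: exponent 1/3. The SAP gives no heart rates or QT values, so all of those below are assumptions. Section 7.5.2 states no numerical result, so there is no plan figure to reproduce.

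**Step 1: size of the literal discrepancy.** The ratio of the fourth-root value to the cube-root value is

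(QT / RR^(1/4)) / (QT / RR^(1/3)) = RR^(1/3 - 1/4) = RR^(1/12),

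which does not depend on QT.

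| HR (bpm) | RR = 60/HR (s) | RR^(1/12) | Relative error |
|---|---|---|---|
| 50 | 1.200 | 1.0153 | +1.5% |
| 60 | 1.000 | 1.0000 | 0% |
| 70 | 0.857 | 0.9872 | -1.3% |
| 75 | 0.800 | 0.9816 | -1.8% |
| 80 | 0.750 | 0.9763 | -2.4% |

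**Step 2: false change from baseline within an arm.** Hold the true QTcF at Q. The artefact is Q × [RR1^(1/12) - RR0^(1/12)]. With Q = 410 ms:

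- 70 to 75 bpm: -2.3 ms (-2.2 to -2.4 ms for Q from 390 to 430 ms).
- 70 to 80 bpm: -4.5 ms (-4.3 to -4.7 ms over the same range).

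**Step 3: false difference between arms.** Every arm would use the same formula, so only a difference in heart-rate change matters. With Q = 410 ms and both arms starting at 70 bpm:

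- both rise 5 bpm: 0.0 ms;
- one rises 5, the other 3: -0.9 ms;
- one rises 5, the other 0: -2.3 ms;
- one rises 10, the other 0: -4.5 ms.

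So a fourth root, if it were really applied, would give different numbers.

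**Step 4: is the fourth root the plan's instruction?** Set the evidence side by side.

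- *For the cube root:* the method is named in Section 7.5.2, the result carries that method's label, and the abbreviation list repeats the name.
- *For the fourth root:* one root index in the extracted equation. No sentence calls it a modification, no reason is given, and no other section repeats it.

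A root index is a very small glyph, easily misread in conversion from PDF. This is the only indexed root in the SAP. The joint-count formulas in Section 6.1.1 use plain fractions, and the DAS28(CRP) formula in Section 6.2.1 uses plain square roots, so their clean conversion does not vouch for this character. The extracted text also has a probable single-character misread elsewhere: in Appendix 2 infliximab appears partly in lower case within a list that is otherwise all capitals.

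**Step 5: where the value goes.** It feeds by-visit values and changes from baseline, summarized descriptively. Uncorrected QT, RR and pulse are summarized as well, so the heart-rate shifts needed to produce the Step 3 differences would be visible.

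**The case for a change.** The strongest case for the concern is that the equation is the operative instruction. The method name does not print an exponent, the equation does, and a programmer may code what is displayed. The joint-count and DAS28(CRP) formulas came through the conversion legibly, so a misread here is not proven, and a drafting slip is possible too. The direction of the error would also be unwelcome in a safety review, because understating QTcF as heart rate rises works against detecting prolongation.

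Part of this stands. The extracted text does show 4, 4 does not match the named correction, and the RR^(1/12) arithmetic is right. A drafting slip cannot be excluded from the text alone.

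It does not stand as a finding against the plan. The conflict is between an unambiguous method name and one doubtful glyph, not between two statements of the SAP. Nothing else in the document can settle which character is on the page. If the page shows 3, nothing is wrong and nothing needs to change. The step from the glyph to wrong output also requires someone to program a fourth root under the label QTcF, against the name of a standard correction, and nothing in the SAP points that way.

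**Conclusion.** No error in the plan is established. The SAP fixes the Fridericia correction by name in Section 7.5.2 and in the list of abbreviations, with RR defined in seconds as that formula needs. The apparent fourth root rests on a single character that conversion from PDF may have altered.

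The conclusion assumes that analysts apply the correction the SAP names. The page image of Section 7.5.2 would show the printed index directly. If it were 4, the matter would be a one-character slip in a displayed equation, with the intended method still clear from the text. Programmed literally, it would shift values by -1.3% at 70 bpm and -2.4% at 80 bpm, and would shift the difference between arms by 0.0 to -4.5 ms across the assumed heart-rate scenarios at 410 ms. All of that would fall on descriptive ECG summaries; no test, efficacy endpoint or stated QTcF threshold would be affected.
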